As part of the screening process, clinical histories, physical examinations including vital signs, and photography of sun exposed and non sun-exposed arm will be performed. Cutometry, Raman spectroscopy (Biophotonic scanning) and transepidermal water loss will be measured.

Enrollment Visit (VISIT 2—subset of 30 participants from the older group above will be invited for this visit)

Upon enrollment into the study, patients will be instructed on proper usage topical retinol versus vehicle placebo. The placebo versus treatment arm will be clearly labeled on the subject's diary to minimize subject error. Participants will apply treatment to one arm and placebo to the other arm based on computer generated randomized assignment of left or right for the retinol. Participants are blinded to the treatment. Participants will be given a diary to record adherence to study procedures. Participants will be instructed to discontinue study if there is any itching or burning sensation that is moderate or severe and to contact study personnel immediately should this occur.

Week 12 visit (VISIT 3—the 30 participants from VISIT 2 (older group) only)

Adverse events and concomitant medication changes will be assessed and recorded. Study diary will be reviewed for adherence to study regimen. Photographs, cutometry and TEWL measurements will be taken. Two 4 mm skin biopsies will be taken at this time, one from the side with the retinol exposure and one from the side without retinol exposure after injection of a small amount of lidocaine anesthetic. Skin biopsies will be bisected and placed in either formalin for hematoxylin and eosin staining and mucin staining (for GAG), or placed into RNA later for subsequent gene expression analysis by 3'-end sequencing as described in Chang et al., 2013. Tissue will also be sent for microRNA analysis.

VISIT 1—age<25 years group only

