As part of the screening process, clinical histories, physical examinations including vital signs, and photography of face, sun exposed and non sun-exposed arm skin will be performed. Cutometry, Raman spectroscopy (non invasive Biophotonic scanning) and transepidermal water loss will be measured. Photographs, cutometry and TEWL measurements will be taken. A 4 mm skin biopsies will be taken from the inner arm skin after injection of a small amount of lidocaine anesthetic. Skin biopsies will be bisected and placed in either formalin for hematoxylin and eosin staining and mucin staining (for GAG), or placed into RNA later for subsequent gene expression analysis by 3'-end sequencing as described in Chang *et al.*, 2013. Tissue will also be sent for microRNA analysis.

Statistical Considerations

This study is powered using data from Kafi et al. for the primary clinical endpoint of fine

wrinkling score as measured by semi-quantitative scale of 0 to 9. A sample size of 36 provides a power level of 0.80 in detecting a difference of 1.00 unit on mean value before and after treatment for the fine wrinkling scale, with a type I error rate of 0.05 for a 2-tailed hypothesis, assuming a standard deviation of differences to be 1.8. Assuming a dropout rate of 10%, the sample size needed is 28 subjects.

Anticipated Results

Results of photographs will be analyzed in blinded fashion by a board certified dermatologist for skin aging parameters including fine wrinkling (tertiary endpoint), dyspigmentation, and surface texture with results graded on a 9 point Likert scale per Kafi *et al.* We anticipate that there will be statistically significant differences in mean score of these parameters between pre- and post- treatment groups for both vitamin A and placebo.

Results of histology will be evaluated in blinded fashion by a dermatopathologist. Parameters of skin aging will include measurement of epidermal thickness, and density of collagen and elastin. Results from the pre- and post- treatments groups for topical vitamin A versus placebo will be compared.

Results of the cutometry and TEWL measurements will be grouped and mean and standard deviations for the older patients before and after topical vitamin A treatment will be calculated and compared to placebo. We anticipate there will be statistically significant differences in the mean scores in cutometry and TEWL measurements between treated and placebo groups.

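### No retinol-versus-vehicle estimator adjusted for the baseline arm difference is defined for measures taken at both visits; defining one is cheap, though the gain in precision is uncertain

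*Combined protocol and SAP*

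**What the plan says.** Under Enrollment Visit (VISIT 2), each woman treats one arm with retinol and the other with vehicle, by "computer generated randomized assignment of left or right for the retinol". Photographs, cutometry and TEWL are taken at screening (Visit 1) and again at Week 12. The older group is biopsied at Week 12 only.

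The analysis text is all before/after:

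- Statistical Considerations powers the study for "a difference of 1.00 unit on mean value before and after treatment for the fine wrinkling scale", "assuming a standard deviation of differences to be 1.8".
- Anticipated Results, photographs (fine wrinkling included): significant differences are expected between pre- and post-treatment scores, separately for vitamin A and for placebo.
- Anticipated Results, cutometry and TEWL: "mean and standard deviations for the older patients before and after topical vitamin A treatment will be calculated and compared to placebo". Differences between treated and placebo groups are expected.

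The document names no test, regression model or covariate for any of these measures.

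**The concern.** The randomised comparison in this design is retinol arm against vehicle arm within the same woman. For fine wrinkling the plan never states that contrast. It describes change within each product and expects change on placebo too, so a pre/post difference on retinol cannot by itself be credited to retinol. For cutometry and TEWL the comparison with placebo is mentioned but not defined.

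The Visit 1 readings can enter the contrast in different ways. Because side is randomised, the expected baseline difference between arms is zero, so subtracting it in full is not needed for an unbiased estimate and can add noise. Using it as a covariate lets the data decide how much to subtract. With about 27 completers, leaving this open may waste precision, and it allows the analysis to be chosen after the results are seen.

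**Working it through.** **Inputs from the document.** Difference 1.00; SD of differences 1.8; two-sided 0.05; 30 women invited to Visit 2; 10% dropout, so 30 × 0.9 = 27 completers; wrinkling scale 0 to 9, with entry at 7 or more.

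**Assumptions not in the document.** The SD of 1.8 applies to the retinol-minus-vehicle difference in change. r is the correlation across women between the Visit 1 and Week 12 arm differences, taken as 0.2 to 0.6. s0 and s1 are the SDs of those two differences.

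**The plan's own figure.** It says "A sample size of 36 provides a power level of 0.80". The paired normal formula gives (1.8 × (1.960 + 0.842))² = 25.4, so 26. The exact paired t-test needs 28 (power 0.81), and 36 gives 0.90. The stated 36 does not reproduce. That is a separate matter; the calculations below use 27 completers, for which the paired t-test on change has power 0.79 and standard error 1.8/√27 = 0.346.

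**Variance formulas.**

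- Change score: s0² + s1² − 2·r·s0·s1.
- Adjusted for the baseline difference: s1²(1 − r²).
- Change minus adjusted: (s0 − r·s1)², which is never negative in large samples.
- Estimating the slope multiplies the adjusted variance by (n−2)/(n−3) = 25/24 at n = 27. The test then has 25 degrees of freedom.

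**Equal SDs (s0 = s1).** The large-sample ratio is (1 − r²)/(2(1 − r)) = (1 + r)/2.

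| r | s0 = 1.8/√(2(1−r)) | ratio | × 25/24 | power |
|---|---|---|---|---|
| 0.2 | 1.42 | 0.60 | 0.625 | 0.94 |
| 0.4 | 1.64 | 0.70 | 0.729 | 0.90 |
| 0.6 | 2.01 | 0.80 | 0.833 | 0.86 |

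Break-even at n = 27 is where (1 + r)/2 × 25/24 = 1, that is r = 0.92.

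**Narrower baseline spread, as entry at 7 or more could cause for wrinkling.** If both arms had to score 7 to 9 (the criterion does not say so), the baseline difference would lie within ±2 and its SD could not exceed 2.0. The 2.01 needed at r = 0.6 above would then be impossible. Two illustrative values of s0 are used: 0.8, and 1.15 (two independent arms, each equally likely to score 7, 8 or 9: variance 2/3 + 2/3 = 1.33). The change SD stays at 1.8, so s1 = r·s0 + √(3.24 − s0²(1 − r²)), and the ratio is s1²(1 − r²)/3.24.

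| s0 | r | s1 | ratio | × 25/24 | power |
|---|---|---|---|---|---|
| 0.8 | 0.2 | 1.78 | 0.94 | 0.98 | 0.80 |
| 0.8 | 0.4 | 1.96 | 1.00 | 1.04 | 0.78 |
| 0.8 | 0.6 | 2.16 | 0.92 | 0.96 | 0.81 |
| 1.15 | 0.2 | 1.63 | 0.79 | 0.82 | 0.86 |
| 1.15 | 0.4 | 1.92 | 0.95 | 0.99 | 0.79 |
| 1.15 | 0.6 | 2.24 | 0.99 | 1.03 | 0.78 |

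Simulation of the adjusted test agreed with the power columns of both tables to within 0.01, and the estimates were unbiased.

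**Side.** A left-right effect of ±0.25 unit on the change difference explains 0.0625/3.24 = 1.9% of its variance; ±0.5 unit explains 0.25/3.24 = 7.7%. With no such effect and equal SDs at r = 0.5, adding a side term lowers power from 0.88 to 0.87.

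**The case against.** Four objections have force.

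- **The plan does not commit to a change score.** The wording is descriptive, so a reader who infers that the planned analysis is inefficient is criticising an estimator the document never states. This stands. What the document supports is that the estimator is undefined.
- **The power gain can be oversold.** A reader might infer that adjustment lifts power from 0.79 to 0.86–0.94. That needs the arm difference to vary as much at Visit 1 as at Week 12, which is doubtful for wrinkling under the entry rule. It also takes 1.8 from a before/after difference and applies it to a between-arm contrast. If 1.8 is the SD of change in one arm and the two arms' changes correlate at 0, 0.3, 0.5 or 0.7, the contrast SD, 1.8 × √(2(1 − correlation)), is 2.55, 2.13, 1.80 or 1.39, and change-score power at 27 is 0.50, 0.65, 0.79 or 0.95.
- **Baselines on both arms are not stated.** Screening mentions photographs of sun-exposed and non-exposed arm skin and gives no site for cutometry or TEWL. Yet the plan's own before/after comparison with placebo cannot be made without a reading on each inner arm, so this is a gap in wording to close.
- **Omitting side does not bias the estimate.** A reader might infer bias from an uneven left/right split. Side is randomised, so any imbalance is chance. A within-woman change already cancels a constant left-right difference, nothing in the document suggests that side alters response, and blocking is not ruled out.

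Unadjusted paired change would be valid. The entry floor does not apply directly to cutometry or TEWL, where equal SDs are easier to defend.

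**Conclusion.** The point holds as a gap in definition with a modest, conditional gain in efficiency. For the three kinds of measure taken at both visits, no baseline-adjusted retinol-versus-vehicle estimator is named, and for fine wrinkling the between-product contrast itself is missing.

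With equal SDs, adjustment cuts large-sample variance by 20% to 40% for r between 0.6 and 0.2. This ratio does not depend on the 1.8. With a restricted wrinkling baseline the result lies between a loss of about two points of power and a gain of about seven (0.78 to 0.86 against 0.79). Neither r nor the SDs at the two visits is given, so no single figure should be quoted. The document does not support a claim of a definite loss of power, or of bias from leaving side out.

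The point does not extend to histology or gene expression, where the older group has no baseline sample to adjust for.

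**What to change.** Add to Statistical Considerations, for photographic scores, cutometry and TEWL:

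- The effect is each woman's Week 12 retinol-minus-vehicle difference, regressed on her Visit 1 retinol-minus-vehicle difference. The estimate is the intercept at zero baseline difference, reported with a 95% confidence interval.
- Visit 1 readings are recorded on both inner arms, at the sites measured again at Week 12.
- A side term is left out, or named in advance as a sensitivity analysis only.

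Any power statement for this contrast should give its assumed r and SDs as a range.

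The cost is a few lines of text and one degree of freedom. If only one inner arm was to be measured at Visit 1, a second set of readings is needed, but the plan's comparison with placebo needs those in any case.

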Formulation of topical retinol per Kafi *et al.* by combining a 41% retinol solution in 55% polysorbate 20 in sufficient proportions with fragrance-free Norwegian Formula Neutrogena Body Moisturizer (Ortho-Neutrogena Co, Los Angeles, Calif) to yield a 0.4% retinol lotion. The vehicle was similarly prepared with 55% polysorbate 20 solution in Norwegian Formula Neutrogena Body Moisturizer. There were no discernable differences in color, odor, or consistency between the active lotion with retinol and the placebo lotion control. A stability study using high-performance liquid chromatography will be performed to demonstrate that more than 90% of 0.4% retinol remained in the moisturizer 3 months after preparation. Both 0.4% retinol lotion and its vehicle were placed in dark glass containers covered with foil to eliminate transmission of UV radiation and stored at 4°C.

After Stanford Human Subjects Panel approval and written informed consent, participants will be screened for eligibility as follows:

Inclusion Criteria

Able to provide written informed consent Older group: Age between 50 and 75 years Young group: Age less than or equal to 25 years Female

Fine wrinkling score at baseline =7 or greater if in older group
All 4 grandparents of Han Chinese, Korean or Japanese descent
Willing and able to apply topical agents to inner arms
Uncontrolled medical problems including diabetes, active chemotherapy
Body mass index within normal or overweight range
No history of weight loss of >20 lbs. within past 5 years

Exclusion Criteria

Skin condition in the areas of skin biopsy that would obscure results of analysis
Topical creams or treatment to arms 2 weeks prior to study baseline visit, including
sunscreens, topical moisturizers, sunless tanners
Individuals with known hypersensitivity to retinoid class of agents
Prior anti-aging treatments to arms including retinol, microdermabrasion within 2 weeks of
baseline visit

Confidential Stanford University School of Medicine

Prior laser therapy or surgical procedure to arms
Prior radiation or other trauma (extensive burns or abrasions) to arm skin
Hormone-based therapy within 4 weeks of enrollment

Screening Visit (VISIT 1—older group only)

Only individuals fulfilling eligibility criteria will be enrolled.

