Whole transcriptome libraries will be created from the samples stored in RNA later and sent for 3'-end sequencing at Stanford Functional Genomics Core Facility after de-identification. We have utilized this Core facility for other projects in the past with high quality results. Results will be analyzed by our bioinformatician using the methods outlined in Chang ALS *et al.*, 2013. Specifically, comparisons will be made in skin from older participants between the pre and post treatment compared to placebo. All results of interest from 3'-end sequencing will be confirmed by RT-qPCR.

We anticipate that the adverse event rate (deemed related to study agent by investigator) for participants is less than 10% and may include mild (grade 1) itching or burning.

Significance

This study will be the first broad based, unbiased investigation into the molecular basis of the anti-aging effects of topical vitamin A. This study is a high quality, well-controlled study using state-of-the art technology of 3-Seq and microRNA analysis. Our research group has established the workflow from previous larger studies in skin aging (unpublished data) and can now leverage this experience for maximal efficiency and positive results. Specifically, we would be able to compare our results to inner arm skin from females younger than 30 years whose gene expression profiles are already contained in our database.

Confidential Stanford University School of Medicine

This study will provide novel candidate gene pathways as well as confirm suspected/known genes important for skin rejuvenation in humans. This information will aid in discovery of new topical agents that might have rejuvenative capacity due to their ability to mimic aspects of the vitamin A gene expression changes.

References

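### The sequencing (Aim 1) and histology analyses are written as pre- versus post-treatment comparisons, but no older participant has a pre-treatment biopsy

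*Combined protocol and SAP*

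**What the plan says.** The plan is a single combined protocol and SAP. Under Anticipated Results, the transcriptome paragraph defines the gene-expression analysis: "comparisons will be made in skin from older participants between the pre and post treatment compared to placebo". The histology paragraph of the same section says: "Results from the pre- and post- treatments groups for topical vitamin A versus placebo will be compared". The material for sequencing is the stored biopsy tissue: "Whole transcriptome libraries will be created from the samples stored in RNA later".

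The visit descriptions under Materials and Methods say when tissue is taken.

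- **Older group, Visit 1**, headed "Screening Visit (VISIT 1—older group only": history and examination, then "photography of sun exposed and non sun-exposed arm will be performed" and "Cutometry, Raman spectroscopy (Biophotonic scanning) and transepidermal water loss will be measured". No biopsy is listed.
- **Older group, Visit 2 (enrolment)**: instruction, randomised side and diary. No biopsy is listed.
- **Older group, Visit 3 (week 12)**: "Two 4 mm skin biopsies will be taken at this time, one from the side with the retinol exposure", the other coming from the side without retinol.
- **Young group, Visit 1**: "A 4 mm skin biopsies will be taken from the inner arm skin", followed by the anaesthetic and tissue handling in full.

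**The concern.** A change from before to after treatment needs a sample from before treatment. Both tissue analyses ask for such a change and then for its comparison with placebo, yet every biopsy in the older group is taken after 12 weeks of application.

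This matters because finding molecular pathways is the trial's stated objective and its first specific aim, and the quoted sequencing sentence is the only comparison the plan spells out for it. An analyst cannot carry it out as written and would have to choose another contrast once the data are in. In a transcriptome-wide analysis that choice affects which genes are reported.

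Two other sources of untreated skin are within reach: the young group's biopsies and the existing database profiles of women under 30 mentioned under Significance. If either were used as the missing baseline, the treatment effect would be mixed with differences in age and person and, for the database, possibly in laboratory batch.

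**Working it through.** The plan states no figure to reproduce. The check is a count of tissue samples, followed by a look at what those samples can support.

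**Step 1. Biopsies per participant, by visit**

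| Group and visit | Timing | Biopsies listed |
|---|---|---|
| Older, Visit 1 | before treatment | 0 |
| Older, Visit 2 | before treatment | 0 |
| Older, Visit 3 | week 12 | 2 (one per arm) |
| Young, Visit 1 | untreated | 1 |

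**Step 2. Samples needed against samples available.** A pre/post change on each arm, compared between arms, needs four samples per person: two arms × two times. If one baseline biopsy served both arms, three would do. The schedule provides two, both after treatment.

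**Step 3. Totals for the 30 older participants at Visits 2 and 3**

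- Pre-treatment biopsies: 30 × (0 + 0) = 0.
- Week-12 biopsies: 30 × 2 = 60, which is 30 retinol/vehicle pairs.
- At the 10% dropout assumed under Statistical Considerations: 30 × 0.9 = 27 pairs.
- Pre/post tissue pairs: 0 in either case.

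**Step 4. Is baseline tissue supplied elsewhere?** No. The young-group biopsies and the database profiles come from other people. Photographs, cutometry and TEWL are recorded in the older group at both Visit 1 and Visit 3, so pre/post wording is sound for them. The problem is confined to tissue.

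**Step 5. What the week-12 pairs can show.** With sides randomised, the within-person difference (retinol side minus vehicle side at week 12) estimates the treatment effect without a baseline. For one outcome, at two-sided 0.05 and 80% power, the detectable difference in units of the SD of the paired differences is roughly (1.960 + 0.842)/√n:

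- n = 30: 2.802/5.477 = 0.51; the exact paired-t (noncentral t) calculation gives 0.53.
- n = 27: 2.802/5.196 = 0.54; the exact calculation gives 0.56.

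These values are for a single outcome. Adjusting for many genes would raise them.

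**The case against.** The best case on the other side has four parts.

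1. **It is not certain which text is wrong.** A baseline biopsy may have been intended and left out of the visit descriptions. The young group has only one visit, so the fact that its biopsy is spelled out there is weak evidence that the older group's omission was deliberate. This stands as a caution, and the sponsor should confirm what was meant. It does not remove the conflict: as written, the schedule and the analysis cannot both hold.
2. **Aim 1 does not itself require pre-treatment tissue.** It speaks of expression profiles after retinol, and both tissue sentences mention placebo. This is true, and it is why the aim can still be met. But placebo is named only as the comparator for a pre/post change that cannot be estimated. Neither sentence says that the two week-12 samples from one person will be compared as a pair. The sequencing methods are also deferred to a cited 2013 paper; whatever it specifies, it cannot supply baseline samples that were not taken.
3. **The confounding risk is hypothetical.** The plan limits the sequencing comparison to older participants and mentions the database only as a further comparison. That is fair: the risk arises only if someone fills the gap that way, and the conclusion does not depend on it.
4. **The pair counts are optimistic.** They assume that the 10% dropout applies to the 30 enrolled and that every biopsy half is usable. That is also fair, but it affects the number of pairs and leaves the absence of baseline tissue unchanged.

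**Conclusion.** The concern holds and should be corrected before analysis. The pre/post tissue comparisons for sequencing and histology are computable for 0 of 30 older participants, so 100% of them are unavailable. What fails is the pre/post element only. The randomised, within-person retinol-versus-vehicle comparison at week 12 is available in about 27 to 30 pairs and answers Aim 1 as a between-side difference.

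This rests on reading the visit descriptions as complete. If the sponsor did intend baseline biopsies, the visit descriptions are what is incomplete, and the two parts of the plan still have to be reconciled.

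**What to change.** Confirm that the visit descriptions are complete as to biopsies. On that basis, replace the histology sentence and the sequencing sentence under Anticipated Results with wording such as: *Week-12 retinol-side and vehicle-side biopsies from the same participant will be compared in a paired analysis, with participant as block, for histology, 3'-end sequencing and microRNA.* MicroRNA is included because the plan collects tissue for it but states no comparison.

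Remove the pre/post wording for tissue and limit the tissue conclusions to the retinol-versus-vehicle difference at week 12. State that the young-group and database samples are descriptive references and will not stand in for a baseline.

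**Cost:** a change of text only, with no added biopsy or visit. The trial gives up any claim about change from baseline in tissue and any statement about the effect of the vehicle alone. Without baseline tissue, neither claim was available.
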